## 1 Administrative information

---

### 1.1 Study identifiers

- Protocol Version: 3.0, Date: 18 Aug 2020
- Chinese Trial Registry: ChiCTR1900027785
- ClinicalTrials.gov register Identifier: NCT04140110

### 1.2 Revision history

Version	Date	Details
0.1 (draft)	2 Jun 2022	First draft by [name] adapted from ENCHANTED SAP
0.2 (draft)	16 Jun 2022	New version following review by [name] and [name]
1.0 (final)	21 Jun 2022	Final version

## 2 Introduction

---

### 2.1 Study synopsis

The second, ENhanced Control of Hypertension And Thrombectomy strokE stuDy (ENCHANTED2) is an international, multicentre, prospective, randomised, open-label, blinded-endpoint assessed (PROBE) clinical trial, assessing different approaches to intensities of blood pressure (BP) control in a high-risk patient population with acute stroke. There are two nested substudies evaluating different antithrombotic approaches for secondary prevention. The main objective is to determine the effectiveness of more intensive BP lowering (systolic BP [SBP] target <120 mmHg) as compared to a higher BP management (target SBP 140-180mmHg) on functional outcome in patients who have had successful recanalisation with endovascular (mechanical thrombectomy) therapy (EVT) for acute ischaemic stroke (AIS) due to large vessel occlusion (LVO). The full protocol is currently under peer review with a journal, since submission in May 2022.

### 2.2 Study population

This study is being conducted at approximately 60 hospital sites in China, with plans to include additional sites in Australia and the UK.

#### 2.2.1 *Inclusion Criteria*

- Age ≥18 years
- Diagnosis of AIS with LVO confirmed by brain imaging
- To receive EVT <24 hours after the onset of symptoms, according to local guidelines
- Successful recanalisation (defined by expanded treatment in cerebral infarction [eTICI] score of ≥2b) after EVT (See Appendix 1)
- Sustained SBP ≥140 mmHg (defined as 2 successive readings <10 mins apart) within 3 hours after recanalisation
- Provide written informed consent (or from an approved surrogate).

#### 2.2.2 *Exclusion Criteria*

- Unlikely to potentially benefit from therapy (e.g. advanced dementia) or very high likelihood of death within 24 hours post-EVT, judged by responsible treating clinician
- Other medical illness that might interfere with outcome assessments and follow-up (e.g. known significant pre-stroke disability [modified Rankin scale (mRS) scores 3-5], advanced cancer, and renal failure)
- Definite indication/contraindication to different intensities of BP lowering treatment
- Specific contraindications to any of the BP agents to be used (e.g., patients who are hypersensitive [allergic] to any of the ingredients)

- Patients with aortic isthmus stenosis and arteriovenous shunt (exception: patients with haemodynamically inactive dialysis shunt)
- Women who are lactating
- Currently participating in another trial which would interfere with outcome assessments

## 2.3 Study interventions

### 2.3.1 Randomisation

Randomisation is via a central internet-based system, stratified by site, recanalisation time from onset (<6,  $\geq$  6 hours), neurological impairment on the National Institutes for Health Stroke Scale (NIHSS) at admission (score <17 vs  $\geq$ 17). A minimisation algorithm is used to ensure balance across stratification factors.

### 2.3.2 Study treatment

**Intensive BP lowering group:** to commence intravenous BP lowering therapy immediately after randomisation to the intervention group. The SBP target is <120 mmHg within 1 hour, and to maintain this level for at least 72 hours (or hospital discharge, if earlier).

**Control group:** the patient allocated to this group will receive a higher BP target strategy to maintain SBP level 140-180 mmHg after the EVT procedure. BP lowering treatment can be given only for a SBP level  $>$ 150 mmHg, if required to achieve the target of  $\geq$ 140 mmHg.

## 2.4 Outcomes

### 2.4.1 Primary outcome

- mRS at 90 days after randomisation analysed as an ordinal outcome

### 2.4.2 Secondary outcomes

- Intracerebral haemorrhage (ICH), assessed by CT imaging and adjudicated centrally according to five possible definitions:
  - a) symptomatic ICH (sICH), based on National Institutes of Neurological Diseases and Stroke (NINDS) criteria of brain imaging (or necropsy) confirmed ICH with  $\geq$ 1 points deterioration in NIHSS score or death within 36 hours from baseline
  - b) sICH, defined by Safe Implementation of Thrombolysis in Stroke-Monitoring Study (SITS-MOST) criteria, as large ('type II') parenchymal ICH with  $\geq$ 4 points decline in NIHSS score or death within 36 hours from baseline
  - c) sICH, defined by the new Heidelberg Bleeding Classification (HBC) criteria, the details of which are outlined in Appendix 1. *This will be the primary safety measure.*
  - d) ICH of any type in brain imaging  $\leq$ 7 days of treatment

- e) any sICH after EVT within 90 days
- Imaging outcomes
  - a) infarct size assessed by any form of brain imaging (MRI or CT) at 48±24 hours
  - b) oedema size assessed by MRI or by CT during days 2-7
- Death or dependency, measured by NIHSS at 7 days
- The followings at 90 days:
  - Death or major disability (mRS 0-2 vs mRS 3-6)
  - Death and disability as separate categories (mRS 0-2 vs mRS 3-5 vs mRS 6)
  - Health-related quality of life (HRQoL) using EuroQoL EQ-5D-3L scale
  - Duration of hospitalisation
  - Residence
  - Hospital service cost (part of separate health economic analysis)

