6.8. Study Outcomes

Primary outcome

Functional outcomes defined as a shift (improvement) in scores on the mRS at 90 days (3 months). The mRS is a widely used instrument for grading the impact of stroke treatments, with scaling of: 0 = no symptoms at all; 1 = no significant disability despite symptoms, but able to carry out all usual duties and activities; 2 = slight disability, unable to carry out all

previous activities but able to look after own affairs without assistance; 3 = moderate disability requiring some help, but able to walk without assistance; 4 = moderate-severe disability, unable to walk without assistance and unable to attend to own bodily needs without assistance; 5 = severe disability, bedridden incontinent, and requiring constant nursing care and attention; 6 = dead.

Secondary outcomes are:

- 1) ICH: a) sICH, based on National Institutes of Neurological Diseases and Stroke (NINDS) criteria of brain imaging (or necropsy) confirmed ICH with ≥ 1 points deterioration in NIHSS score or death within 36 hours from baseline; b) sICH, defined by Safe Implementation of Thrombolysis in Stroke-Monitoring Study (SITS-MOST) criteria, as large ('type II') parenchymal ICH with ≥ 4 points decline in NIHSS score or death within 36 hours from baseline; c) sICH, defined by the new Heidelberg Bleeding Classification (HBC) criteria; d) ICH of any type in brain imaging ≤ 7 days of treatment; e) any symptomatic ICH (sICH) after MT within 90 days. ICH will be assessed by CT imaging and adjudicated centrally.³³
- 2) Imaging endpoints: a) infarct size growth assessed by MRI at 48 hours; b) edema volume assessed by CT at Day 7.
- 3) Death or dependency measured by NIHSS at 7 days;
- 4) The followings at 90 days: Death or major disability (mRS 3-6); separately on death and disability (mRS 3-5); health-related quality of life (HRQoL) using EQ-5D; duration of hospitalisation; residence and hospital service cost.

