6.10 Data Collection and Follow-up

Registration, baseline assessment, and randomisation should be achieved over 15 minutes. Doctor/nursing attendance with the randomised patient is likely to be required for 1-2 hours post-randomisation to ensure the titration of BP lowering in the active group, and consistent BP recordings. All patients are followed daily for 1 week, and then 90 days unless death occurs earlier. Key demographic and clinical data will be collected at randomisation. Follow-up data will be collected on 3 occasions: 24 hours, 7 days (or hospital discharge if sooner), and 90 days. The 90 day evaluations will be conducted in-person or by telephone, by a trained staff member at the local site who is blind to the treatment allocation. Brain imaging (CT scan and/or MRI, with any associated diffusion/perfusion and angiogram images) will be conducted according to standardized techniques at baseline, within 24-48 hours (ie next day follow-up scan), and at a later stage in all surviving patients who may deteriorate or for other clinical

reason during follow-up. Brain imaging (CT scan and/or MRI) must be uploaded to the ENCHANTED2 server, either directly from the hospital site (if they have suitable broadband internet) or via the RCC office, to be analyzed centrally for measurement of any ICH or haemorrhagic complications of the ischemic lesion, and for future measurement of areas of infarction, ischemic penumbra, and site of LVO. The LCC will keep a hard copy in an uncompressed DICOM format onto a CD-ROM for monitor site verification (**see Appendix 3**). Trial management is facilitated by an established internet-based system.

All randomised patients will be followed up to 90 days, or death if prior to 90 days. Patients who do not follow the protocol and/or discontinue allocated management should still be followed up to 90 days as their data will be analyzed on the 'intention to treat' principle. **Table 3** illustrates the schedule and nature of the data collection required during the study period. The paper version of the case reports forms (CRFs) will be supplied with the procedure manual, as a reference only, together with a guide to completion of each data element and a definition of terms.

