6.10.5 Follow up Data

Day 1 (Form C)

The primary goal of assessments within the first 24 hours will be to ensure adherence to the allocated the protocol. BP and administered medication will be recorded. BP will be recorded supine in the non-paretic arm from the automated, electronic device used at the Clinical Centre. BP will be recorded every 15 minutes for the first hour, then hourly for the next 5 hours, and 6 hourly from 6 hours to 24 hours. When i.v. boluses are given, HR and BP should be re-checked and recorded 5 and 15 minutes later. The following information will be recorded.

- BP
- BP lowering medication
- GCS and NIHSS scores at 24 hours
- Follow up brain imaging (CT brain and/or MRI) should be undertaken at 24-48 hours post-MT
- If other imaging investigations are performed (i.e. transcranial Doppler), these should be documented in the CRFs
- Antithrombotic medications
- Follow up blood tests
- Standard stroke care assessment

Day 7 or discharge if earlier (Form D)

On Day 7 or on the day of hospital discharge/transfer or death if prior to Day 7, the contact details of the patient or caregiver should be confirmed to facilitate follow up assessments. The following information will be recorded:

- GCS and NIHSS score
- Dependency assessed with the mRS
- BP
- BP lowering medication (medications used during Days 2 to 7)
- Medications and key specific treatment received during hospitalization
- Other aspects of acute stroke management during hospitalization

- Prognosis prediction from clinicians
- Date of discharge or transfer from hospital
- Repeat brain CT or MRI
- Healthcare costs and details of blood pressure lowering treatment.

BP Monitoring Chart (Form E)

As usual nursing care during the study period, the BP assessments in 7 days will be used to check adherence to BP management protocol.

Day 90 Follow-up (Form F)

These assessments are to be undertaken by an investigator who was not involved in the clinical management of the patient, and blind to the randomised treatment allocation. On 90±7 days, all surviving patients will be evaluated through a telephone interview or at a face-to-face consultation.

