Detailed resource utilization data, hospital billing data, physical function and patient reported quality of life data were collected for patients from the time of randomisation through 90-day follow-up. These data were used to calculate direct healthcare costs and QALY during the initial 90-day period based on international and national guidelines.^{34, 35}

- BP
- Dependency assessed with the mRS³⁶
- HRQoL measured by the EQ-5D³⁷
- Patient living status (e.g. home, high care)
- Any complications or hospitalization since going home
- Any medication currently used
- Healthcare related cost.

Death

Patients who have died prior to any of the above scheduled assessments, cause of death documentation will be collected with date and time of death. Copies of post-mortem reports, hospital record entry or death certificate, should be kept with the Patient Contact Details log to assist in trial monitoring by the CCC. An SAE form is to be completed for all deaths during the study period, stating the primary and underlying cause of death.

Withdrawal of allocated management and protocol violations

A form will be provided to record the date and circumstances surrounding any deviation from the protocol or missed assessments.

Consent

Consent will be documented in the patient's progress notes and CRF and the type(s) of consent obtained will also be recorded on the database.

Serious Adverse Events (SAEs)

All SAEs will be recorded on the SAE form, and completed on the electronic CRF or faxed/mailed from a printed form to the CCC within the prescribed time. Additional information may be requested to provide supplementary information on the event and outcome.

Table 2 Schedule of evaluations

Evaluation	Baseline (Prior Randomisation)	Day			365 ^b
		1	7 ^a	90 ^b	
Eligibility	X				
Brain imaging (CT ± angiogram or MRI± angiogram or DSA)	X	X	X		
BP	X (BP x 2)	X** q 15 min 1h 6h	X q12h	X	
HR	X				
ECG	X				
Consent	X				
Medical history, prior medications	X				
Details of rt-PA (if performed) and MT	X				
Physical exam GCS/ NIHSS	X	X	X		
Functional assessment with mRS	X		X	X	
HRQoL assessment with EQ-5D				X	
Routine blood tests	X	X			
BP lowering treatment		X	X	X	
Antithrombotic and other medications		X	X	X	
Standard stroke care		X	X		
Hospitalized or not			X	X	
Contact details for Follow-up		X	X		
Hospital service cost			X	X	
SAEs	X ^c	X	X	X	X

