Appendix 3 - Imaging protocol

It would be desirable to use the same modality for both pre-randomisation and follow-up imaging from the same subject. However if for technical or practical reasons this is not possible, mixed CT and MR acquisitions (eg CT pre-randomisation and MR follow-up) are acceptable.

CT scans should cover the entire brain from the foramen magnum to the vertex with 4–5 mm thick slices through the posterior fossa and 8–10 mm thick for the cerebral hemispheres, with no slice gap. Scans should be windowed on a width of 80 Hounsfield Units (HU) and a centre level of 35–40 HU. All patients (irrespective of treatment allocation) should have a follow-up scan at 24 hours. In addition a repeat scan is required if the patient deteriorates neurologically or ICH is suspected for any reason.

In addition to the diffusion/perfusion MRI or perfusion CT series, any structural MRI (GRE, T2, FLAIR) or CT (spiral CT, etc) sequences acquired at the same time should be included. For CT, spiral CT is to be preferred over CT MPR data or sequential axial CT acquisitions with thick slices. Suggested acquisition parameters are given in Table A1- A4 below.

If angiography (either MR or CT) have also been acquired, these should be submitted as well. Suggested acquisition parameters are given in Table A5 below.

Table A1. Recommended Acquisition Protocol for Perfusion-CT (PCT)

Acquisition Rate	1 image per second, (ideally at one source rotation per second)
Total Acquisition Time Base Line Period	40 to 60 seconds 5-10 volumes should be acquired prior to contrast arrival
Kvp and	80 kVp (not 120 kVp)
mAs	100 mAs or higher
Contrast Volume	35-50 mL (with saline flush)
Delivery Rate	4-6 mL per second
Coverage	As dictated by configuration of hardware

Table A2. Recommended Acquisition Protocols for Perfusion-Weighted (PWI) MR Imaging

Sequence	Single-shot gradient-echo echoplanar imaging
TR	TR = 1500 to 2000 ms
TE	TE=35 to 45 [contact] TE=25 to 30 ms @ 3T
Flip angle	flip angle =60 to 90° @ 1.5T, 60° @ 3.0T
Baseline	At least 10-12 Baseline images (please note the first few images prior to steady state are discarded)
Coverage	At least 12 slices, with same slice thickness and gap as DWI, increase TR and slice gap to achieve reasonable coverage.

Table A3. Recommended Acquisition Protocols for Diffusion-Weighted (DWI) MR Imaging

Sequence	Single-shot spin-echo echoplanar imaging
TR	Should be at least 4000 ms (but can be larger)
TE	Minimum achievable

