**Table 12. Imaging outcomes**

Outcome	Raw data				Model results	
	Intensive		Guideline		Intensive	Guideline
	BP Control	BP Control	BP Control	BP Control		
Outcome	N	mean (SD)	N	mean (SD)	Mean (SE)	Mean (SE)
Infarct size (mL)						
Baseline	xx	xx.x (xx.xx)	xx	xx.x (xx.xx)		
48 hours	xx	xx.x (xx.xx)	xx	xx.x (xx.xx)	xx.x (xx.xx)	xx.x (xx.xx to xx.xx) 0.xxx
Oedema volume (mL)						
Baseline	xx	xx.x (xx.xx)	xx	xx.x (xx.xx)		
48 hours	xx	xx.x (xx.xx)	xx	xx.x (xx.xx)	xx.x (xx.xx)	xx.x (xx.xx to xx.xx) 0.xxx

*Programming notes:*

- repeat this table in the per-protocol population

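### Oedema is timed three ways and the status of the day-7 scan is unsettled, so late oedema, and to a lesser degree any ICH, can depend on scans ordered by clinicians who know the allocation

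*SAP*

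**What the plan says.** **When oedema is measured.** Protocol 6.8 lists "edema volume assessed by CT at Day 7". SAP 2.4.2 has "oedema size assessed by MRI or by CT during days 2-7". SAP Table 12, under the label beginning "Oedema volume (mL", has rows for baseline and 48 hours only.

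**Whether a late scan is for everyone.** In protocol 6.10.5, Form D (Day 7, or discharge if earlier) includes "Repeat brain CT or MRI" among the items to be recorded, with no condition attached. Table 2, in the row beginning "Brain imaging (CT ± angiogram or MRI± angiogram or DSA", marks baseline, Day 1 and Day 7, and a footnote moves Day 7 to discharge if that is sooner. Section 6.10 instead describes imaging at baseline, within 24-48 hours, "and at a later stage in all surviving patients who may deteriorate or for other clinical" reasons. Appendix 3 says that all patients "should have a follow-up scan at 24 hours", and asks for a repeat only on neurological deterioration or suspected ICH.

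**How the scans are used.** SAP 3.8.4 fits a constrained longitudinal model that takes in every patient with a baseline or a follow-up value. SAP 2.4.2 includes ICH of any type up to 7 days, and 3.8.2 plans no imputed analysis for ICH. The trial is PROBE: treatment is open, and the imaging committee (protocol 13.4) reads scans without knowing arm or scan time.

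**Infarct window.** SAP 2.4.2 gives "infarct size assessed by any form of brain imaging (MRI or CT) at 48±24 hours", with no statement of when the clock starts.

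**The concern.** Haemorrhage and oedema are the pathways through which the trial expects blood pressure lowering to act. Protocol 4.2.3 gives oedema and ICH after reperfusion as the harms of high pressure, and the SAP treats infarct and oedema size as mechanistic outcomes. Separate papers on ICH with infarct growth, and on oedema, are planned in SAP Appendix 3.

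If some patients are scanned late because the schedule says so and others because a clinician was worried, the late value is no longer a measurement on the randomised groups. It is a measurement on those who were selected for a scan. In an open-label trial the threshold for ordering a scan can differ by arm. An apparent difference in oedema or late ICH could then arise without a treatment effect, or a real one could be blurred. Separately, a programmer cannot fill Table 12 from the SAP's definition without choosing a time point, and nothing ensures that the choice is made before unblinding.

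**Working it through.** The plan gives no figure to reproduce. The check sets the passages side by side and follows each reading through to the analysis.

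**1. Oedema time.**
- Protocol 6.8: Day 7, CT.
- SAP 2.4.2: days 2-7, MRI or CT.
- SAP Table 12: 48 hours.

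The SAP is the later document, so it could override the first line. It cannot settle the second against the third, because both are in the same final version.

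**2. Status of the late scan.**
- No trigger: Form D and Table 2.
- Clinical trigger: section 6.10 and Appendix 3.

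Each side has two places in the current protocol. This is not a difference between current and superseded text.

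**3. What reaches the oedema model.**
- *A site following Form D and Table 2.* Every patient still under observation has a scan at day 7 or discharge, and some also have triggered scans. Several scans can fall in days 2-7, and no rule says which one is analysed.
- *A site following 6.10 and Appendix 3.* A stable patient has only the early scan. Whether a scan at 24 h or 36 h belongs to days 2-7 depends on how days are counted, which the SAP does not say. The patient contributes either an early value or none. A patient who deteriorates contributes a later, triggered scan. So either the time of the value or its existence depends on the clinical course and on the decision to scan.

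The model in 3.8.4 has terms for treatment, site, time from onset and baseline NIHSS. It treats missing follow-up values as random given those terms and the baseline measurement. Deterioration after baseline is not among them.

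**4. Form of the bias with no true effect.**
- *Oedema.* Let p be the share who deteriorate (all scanned late, mean M1), and s the share of the remainder scanned late (mean M0). The mean among scanned patients is [p·M1 + (1−p)·s·M0] / [p + (1−p)·s]. It equals the true mean when s = 1, and differs between arms whenever s does and M1 ≠ M0.
- *Any ICH.* Let d be the share whose bleed is first visible after the early scan, and s1 and s0 the probabilities in the two arms that such a bleed is imaged. The false risk difference is d × (s1 − s0).

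None of p, s, M1, M0, d, s1 or s0 is in the documents, so no size can be given. The structure does show the order of exposure. Every patient should have the early scan, so for any ICH only the fraction d is at risk. For oedema defined on a late scan, the whole value is.

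**5. Infarct window.** 48 − 24 = 24 h and 48 + 24 = 72 h, so the lower limit coincides with Appendix 3's target time. Protocol 6.10.5 counts its 24-48 h from MT, and 6.6 allows randomisation up to 3 h after MT. If the SAP clock starts at randomisation, a scan done exactly 24 h after MT can fall at 24 − 3 = 21 h. If it starts at MT, the same scan sits on the limit. If it starts at stroke onset, it is past the limit. The origin needs to be stated.

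**The case against.** The best defence is that the protocol can be read without contradiction: a scan at day 7 or discharge for all, as in Form D and Table 2, with triggered scans on top. Section 6.10 does not use the word only and does not cancel any scheduled scan, and Table 2 was revised in version 3.0. A reader might infer that 6.10 prohibits routine late scans. It does not, so that reading should not be adopted. What stands is that 6.10 and Appendix 3 both set out the imaging and leave out a day-7 scan for all, so a site could follow them in good faith and not do one.

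Second, Table 12 is a proposed shell whose oedema rows repeat the infarct rows, and protocol 10.2 defers analysis detail to the SAP. This is fair as to how the mismatch probably arose. It still has to be resolved, because the shell is what will be programmed.

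Third, readers are blinded, the imaging outcomes are labelled mechanistic, and ICH definitions other than Heidelberg are supportive. All true, and this limits the weight of the point. But blinded reading protects the interpretation of a scan, not the decision to obtain it.

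Fourth, if deterioration itself differs by arm because of treatment, a difference in rescanning partly reflects a real effect. That is correct; only the discretionary part is spurious. The planned analysis cannot separate the two.

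**Conclusion.** The point holds as a conflict of definition that leaves room for selection bias in secondary outcomes. The SAP disagrees with itself on when oedema is measured, the protocol disagrees with itself on whether a late scan is for everyone, and no rule says which scan is analysed. The bias route is open at sites that follow 6.10 and Appendix 3. It is wider for oedema than for any ICH. The 90-day mRS analysis is not touched.

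Three stronger conclusions are tempting and are not supported:
- *That the bias can be given a size in mL or percentage points.* Every input would be invented.
- *That a large share of infarct scans would be lost because they were aimed at 24 h.* This needs a clock origin, a distribution of scan times and a rule discarding early scans; the SAP states none of these.
- *That any ICH is as exposed as oedema.* The early scan for all patients limits its exposure to bleeds that appear later.

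The conclusion assumes that some sites follow 6.10 and Appendix 3 literally, and that the decision to rescan can respond to knowledge of the arm. The documents neither confirm nor exclude either.

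**What to change.** 1. State one oedema time point and window, with its clock origin, in identical terms in protocol 6.8, SAP 2.4.2 and Table 12.
2. Reconcile protocol 6.10 and Appendix 3 with Form D and Table 2 on whether the day-7 or discharge scan is for all patients.
3. In SAP 3.8.4, say which scan is used when a patient has several. Base the main volume analyses on protocol-scheduled scans and keep clinically triggered scans for a supplementary analysis. Do not try to repair the problem by adjusting for scan time: it arises after randomisation and may itself depend on outcome.
4. Add any ICH on the scheduled 24-48 h scan as a sensitivity analysis beside any ICH up to 7 days. Report scan completion, timing and reason by arm.
5. State the clock origin of the infarct window and confirm that scans done at Appendix 3's 24 h target are included.

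Cost: SAP wording, one table shell and a few protocol sentences, best settled before unblinding. The analysis changes need no new scan. If step 2 confirms a scan for all, sites that had been following 6.10 would have to perform it. The reason for each scan must be recorded or retrieved if it is not already captured. The main oedema analysis will use fewer scans, and oedema seen only on triggered scans moves to the supplementary analysis.
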